#### 15.3.6.2. Adverse Events

AEs will be coded using Medical Dictionary for Regulatory Activities (MedDRA).

The summary of AEs for the current study will be limited to those AEs newly occurring on or after the first dose of the OLE (SEP361-309) study drug. AEs carried over from study SEP361-308 will be presented in data listings only.

The following summaries will be provided by MedDRA SOC and PT:

- All AEs (including incidence rate and event count)
- AEs by severity (mild, moderate, severe; including incidence rate)
- AEs by relationship to study drug (related, not related; including incidence rate)

The following conventions will be followed in summarizing AEs:

- For incidence rate summaries, each subject will be counted only once within each SOC and within each PT.
- If a subject reports more than one AE within a PT and/or a SOC, the AE with the highest known severity will be used in the by severity summary. AEs with a missing severity will be assigned to the highest severity.
- For summaries by relationship to study drug, AEs will be grouped as "related" or "not related." AEs assessed as "possible," "probable," or "definite," will be grouped as "related." AEs with a missing relationship to study drug will be regarded as related. If a subject reports more than one AE within the same SOC and PT, and any are related, the AE will be summarized as related.

Summaries of SAEs and AEs leading to discontinuation will also be provided. In addition, summaries of all AEs, SAEs, and AEs leading to discontinuation by modal daily dose will be provided. All AEs starting after the last dose of OLE study drug up to 9 days following the last dose will be summarized separately. Data listings of AEs, SAEs, AEs leading to discontinuation, and deaths will be presented.

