#### **Statistical Methods:**

The analysis of the long-term safety and tolerability, and effectiveness will be based on the Safety population, which includes all subjects who receive at least one dose of study drug during the 24-week treatment period. All data analysis will be performed for the overall treatment group.

AEs, SAEs, and AEs leading to discontinuation will be summarized by the number and percentage of subjects with any AE, and AEs by system organ class and preferred term. AEs will be further summarized by severity and by relationship to study drug. The summary of AEs will be limited to those AEs newly occurring on or after the first dose of the OLE (SEP361-309) study drug. All AEs starting after the last dose of study drug up to 9 days following the last dose will be summarized separately.

Observed values and changes from PS Baseline and OLE Baseline (the EOT visit from Study SEP361-308) in clinical laboratory tests (including hematology, chemistry, urinalysis) and in clinical evaluations (vital signs and 12-lead ECGs) will be summarized descriptively.

The frequency of subjects with suicidal ideation and suicidal behavior based on the C-SSRS will be provided.

Descriptive statistics will be presented on the change from PS Baseline and OLE Baseline in: PANSS total score and subscale scores, CGI-S score, CGI-I score, BNSS total score, PSQI global score, SF-12 score, PSP total score, MSO score, PANSS Marder Factor scores, and UPSM.

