#### 12. SAFETY REPORTING

#### 12.1. Definitions

#### 12.1.1. Adverse Events

An adverse event (AE) is any untoward medical occurrence associated with the use of a drug in humans, whether or not considered drug related.

Untoward medical occurrences that occur between the time of signing the ICF and first drug administration are pre-treatment events. Those that occur after first administration of study drug are considered AEs.

An AE can, therefore, be any unfavorable and unintended sign (including an abnormal laboratory finding), symptom, or disease occurring after the administration of a medicinal (investigational) product, whether or not considered related to the medicinal (investigational) product. AEs may include the onset of new illness and the exacerbation of pre-existing conditions. AEs will be collected from the signing of the ICF to the last study visit (including Follow-up Visit).

The Investigator should attempt to establish a diagnosis of the event based on signs, symptoms, and/or other clinical information. In such cases, the diagnosis should be documented as the AE and not the individual signs/symptoms.

If a subject answers "yes" to "Suicidal Ideation" Item 4 (active suicidal ideation with some intent to act, without specific plan) or Item 5 (active suicidal ideation with specific plan and intent) on any post-Baseline C-SSRS assessment, an associated AE must be reported.

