#### 12.1.2. Serious Adverse Events

A serious adverse event (SAE) is an AE that meets one or more of the following criteria:

- Results in death.
- Is life threatening.
- Requires hospitalization or prolongation of existing hospitalization.
- Results in persistent or significant disability or incapacity.
- Is a congenital anomaly or birth defect.
- Is an important medical event that may jeopardize the subject or may require a medical or surgical intervention to prevent one of the outcomes listed above. Examples of such medical events include allergic bronchospasm requiring intensive treatment in an emergency room (ER) or at home, blood dyscrasias or convulsions that do not result in inpatient hospitalization.

The term "severe" is often used to describe the severity of a specific event (as in mild, moderate, or severe myocardial infarction) (see Section 12.3); the event itself, however, may be of relatively minor medical significance (such as severe headache). This is not the same as "serious," which is based on subject/event outcome or action criteria usually associated with events that pose a threat to a subject's life or functioning as defined by the criteria above.

During the study, if a subject has a hospitalization or procedure (eg, elective surgery) that was scheduled before the study entry, ie, before informed consent for an event/condition that occurred before the study, the hospitalization is considered a therapeutic intervention and not the result of a SAE. However, if the event/condition worsens during the study, it should be reported as an AE (or SAE, if the event/condition results in a serious outcome such as prolongation of hospitalization).

Life-threatening means that the subject was, in the view of the Investigator, at immediate risk of death from the event as it occurred. This definition does not include an event that had it occurred in a more severe form might have caused death.

SAE criteria information will be captured on the CRF.

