#### The frequency of AE:

- Once an isolated episode.
- Intermittent occurs on two or more separate occasions.
- Continuous does not abate from date of onset to date of resolution.

The action taken with the study treatment:

- **Drug Interrupted** Study drug stopped temporarily.
- **Drug Withdrawn** Study drug stopped permanently.
- Dose Reduced
- Dose Increased
- Dose Not Changed
- Not Applicable
- Unknown

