#### 13. TERMINATION OF SUBJECT FROM STUDY

# **13.1.** Criteria for Subject Termination

Subjects may be discontinued from study participation / the study drug at any time for any of the following reasons. The possible reasons for termination of study participation / study drug are as follows:

- Adverse event
- Lack of efficacy (specify)
- Lost to follow-up (specify)
- Withdrawal by subject (specify)
- Non-compliance with study drug (specify)
- Protocol deviation (specify)
- Death
- Pregnancy
- Other (specify)

If at any time during the course of the study, in the opinion of the Investigator, the subject may no longer safely participate due to a change in medical status (eg, experiences an AE, becomes pregnant), the subject must be discontinued from the study drug. Subjects discontinued from study drug will be discontinued from the study.

The reason for discontinuation of "Lack of efficacy" should be selected when a subject early terminates from the study because there has been insufficient therapeutic benefit of the study drug (perceived or actual) and the subject's baseline condition has neither worsened nor improved significantly.

The reason for study drug discontinuation will be recorded on the appropriate CRF. In case of death, the date of death should be captured on the CRF. Subjects who prematurely terminate the study participation will not be replaced.

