# 15.3.1. Subject Disposition

Subject disposition will be summarized and presented for the number and percentage of subjects who entered the extension study, received at least one dose of the open-label extension study drug, and completed or discontinued from the open-label extension treatment period (including reasons for discontinuation).

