#### 15.3.6. Safety Analyses

#### 15.3.6.1. Analysis of Primary Endpoint

The primary endpoint is the incidence of overall AEs, SAEs, and AEs leading to discontinuation. The incidence will be calculated by a proportion consisting of the number of subjects who experience these events (ie, AEs, SAEs, and AEs leading to discontinuation) as the numerator over the safety population as the denominator along with a corresponding 95% confidence interval (CI).

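### An AE carried over from SEP361-308 that does not worsen but ends OLE treatment is left out of the primary AE-discontinuation incidence

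*Protocol*

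**What the plan says.** **Primary endpoint.** Protocol Section 15.3.6.1 names three components: AEs of any kind, SAEs, and AEs that lead to discontinuation. The section then states how they are computed: "The incidence will be calculated by a proportion consisting of the number of subjects who experience these events", divided by the safety population, with a 95% CI. This section does not itself give an onset limit.

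**Which AEs are summarised.** Section 15.3.6.2 restricts the AE summary to events that are new on or after the first extension dose, and then says "AEs carried over from study SEP361-308 will be presented in data listings only". In the synopsis, under Statistical Methods, the paragraph that opens with AEs, SAEs and AEs leading to discontinuation goes on: "The summary of AEs will be limited to those AEs newly occurring on or after the first dose of the OLE (SEP361-309) study drug". No exception is made for discontinuations.

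**Disposition.** Section 15.3.1 tabulates subjects who "completed or discontinued from the open-label extension treatment period (including reasons for discontinuation"). Adverse event is one of the reasons in Section 13.1, and no onset limit is attached. Section 13.1 also says "Subjects discontinued from study drug will be discontinued from the study".

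**Recording.** Footnote o of Table 2 has AEs that began in SEP361-308 and are still ongoing entered in the extension eCRF. Section 12.3 has action taken evaluated for each AE; one category, drug withdrawn, is defined as "Study drug stopped permanently".

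**The concern.** Only subjects who completed SEP361-308 can enrol (Section 7.1), and they start on the same drug at the same dose (Section 10.1.1). Some may enter with an AE still ongoing; the protocol expects this, since it has such AEs entered in the eCRF. If a subject tolerates the event for some weeks and then stops because of it, that is a failure of long-term tolerability, which is what the primary objective sets out to measure. The event began earlier, but the withdrawal is new and happens on extension drug.

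Under the stated rule this withdrawal is not counted in the primary AE-discontinuation incidence. As a completer of SEP361-308, the subject did not discontinue that study for an AE either. The withdrawal would then be in neither study's AE-discontinuation count. The 95% CI gives no warning of this, because the omission comes from a definition and not from sampling variation.

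**Working it through.** **1. Trace one subject through the rules.** The AE starts in SEP361-308, is ongoing at extension entry, and later leads to permanent withdrawal of extension drug.

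- *If the AE worsens:* Section 12.1.1 says "AEs may include the onset of new illness and the exacerbation of pre-existing conditions". The worsening can be recorded as an AE in this study and counted. This case is not part of the point. (Section 12.1.2 also mentions worsening, but there it concerns hospitalisations or procedures scheduled before consent, so it is not relied on here.)
- *If the AE does not worsen:* there is no new onset. Section 15.3.6.2 sends the event to listings, so it does not enter the numerator.
- *Disposition:* the subject has left the extension, and the reason can be recorded as adverse event. Section 15.3.1 counts it whatever the onset date.

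The disposition count for adverse event can therefore exceed the primary-endpoint count.

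**2. Reproduce the planned denominator.** Inputs from the synopsis (Number of Subjects) and Section 15.1: 120 planned in SEP361-308, 75% completing, 75% of completers enrolling.

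120 × 0.75 × 0.75 = 67.5, stated as approximately 67. The figure reproduces.

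**3. Cost per omitted subject.** With all 67 dosed:

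- 1 omitted: 1/67 = 1.5 percentage points
- 2 omitted: 2/67 = 3.0 percentage points

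**4. Effect on the reported rate.** The protocol gives no expected number of AE withdrawals and no number carried over. The totals below are assumptions that span a range. The intervals are exact (Clopper-Pearson), also an assumption, because the protocol names no CI method. Each row omits one subject.

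| Assumed total AE withdrawals | All counted | One carried-over case omitted |
|---|---|---|
| 1 | 1/67 = 1.5% (0.0 to 8.0) | 0/67 = 0% (0 to 5.4) |
| 6 | 6/67 = 9.0% (3.4 to 18.5) | 5/67 = 7.5% (2.5 to 16.6) |
| 12 | 12/67 = 17.9% (9.6 to 29.2) | 11/67 = 16.4% (8.5 to 27.5) |

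The loss in percentage points is the same in each row. If no subject is affected, the rate is unchanged.

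**The case against.** **It is a stated and usual convention.** Limiting AE summaries to new-onset events avoids counting the same event in both studies, and the synopsis and Section 15.3.6.2 agree with each other. This stands for overall AE incidence. A reader might infer that the onset rule itself is wrong or that the protocol contradicts itself; the text supports neither. The weakness is only that the rule has no exception for a component whose defining event, the stop, occurs in the extension.

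**Section 15.3.6.1 does not repeat the limit.** True, so applying it to the primary numerator takes a step of inference. The step is short. The synopsis puts the limit in the paragraph that covers AEs leading to discontinuation, and the listings-only rule leaves no place for a table count. If the primary analysis was meant to be unrestricted, the sections need reconciling. An unseen SAP could add detail, but one that counted these cases would depart from the protocol's rule.

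**The withdrawals are visible elsewhere.** This also stands. A reader might infer that they are hidden, but the disposition table can count them and the listings show the events. What is affected is the headline rate and its CI.

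**The case is narrow.** The subject must have completed SEP361-308, chosen to continue the same drug, met the entry criteria, had no worsening, and still stopped although dose reductions are permitted. Nothing in the protocol suggests that this is common. A reader might infer a material bias; the documents give no count to support one.

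**Conclusion.** The point holds in limited form. As written, a carried-over AE that does not worsen but leads to withdrawal of extension drug is left out of one of the three primary incidences, while the disposition table can show the subject as discontinued for an adverse event. The effect can only be downward and is 1.5 percentage points per affected subject, assuming 67 subjects in the safety population. The number affected cannot be known from the protocol and may be zero.

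This rests on reading the onset limit in the synopsis and Section 15.3.6.2 as applying to the primary numerator in Section 15.3.6.1. The sample size has no statistical basis and the analyses are descriptive, so no test or decision rule changes. It is still worth correcting, because it concerns a primary tolerability figure in a same-drug extension and the remedy is small.

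**What to change.** In Sections 15.3.6.1 and 15.3.6.2 and the synopsis:

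1. Keep the new-onset limit for the overall AE tables.
2. Report AEs leading to discontinuation of extension drug on two lines, new-onset and carried over from SEP361-308, plus their total with a 95% CI. The new-onset line preserves the figure that the present rule gives.
3. Reconcile the total with the disposition count for adverse event, and explain any difference.
4. State that action taken is to be updated on carried-over AE records. Section 12.3 has it evaluated for each AE, but the protocol does not expressly say that a record begun in SEP361-308 is updated when extension drug is stopped.
5. Footnote that carried-over cases are not in the overall AE count.

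The cost is wording, one derivation flag, an extra table line, one footnote and a recording instruction to sites. The reported rate may be slightly less favourable, and the discontinuation total need not be a subset of overall AEs, which is why the footnote is needed.

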### 7. INVESTIGATIONAL PLAN

## 7.1. Overall Study Design

This is a 24-week, outpatient, multicenter, flexible-dose, open-label extension study designed to evaluate the long-term safety and tolerability of SEP-363856 (50 to 100 mg/day) for the treatment of subjects with schizophrenia who have completed Study SEP361-308 treatment period, during which they were switched from a previous antipsychotic treatment to SEP-363856.

The study will consist of two periods: An open-label extension (OLE) Treatment Period (up to 24 weeks), and a Follow-up Period visit at  $7 \pm 2$  days after last study drug dose for subjects who complete the Treatment Period and those who prematurely discontinue from the study (Figure 1).

Subjects who meet the entry criteria and choose to enter the extension study will transition immediately at the End of Treatment (EOT) visit from Study SEP361-308. Subjects who early terminate (ET) from the SEP361-308 study are not eligible to enroll in SEP361-309. The EOT visit from Study SEP361-308 will serve as the OLE Baseline visit for the present study. Informed consent will be obtained from all subjects before any study procedures are performed for the present study.

A study schematic is presented in Figure 1. Details of the study assessments and other procedures to be performed at each visit are presented in Table 2 Schedule of Assessments, and Section 11.6, Study Visits and Assessments. If necessary, subjects may return to the clinic at any time for an unscheduled visit at the discretion of the investigator.

Subjects will attend a Baseline visit on Day 1 (same day as the EOT visit of Study SEP361-308). Subjects will be seen at Baseline and then every 4 weeks thereafter up to Week 24. Telephone calls will be made by a qualified member of the clinical research staff to the subjects weekly between visits to administer the C-SSRS, collect AEs and concomitant medications, as well as to remind subjects about adherence to study drug administration and upcoming visits.

[figure not shown]

Figure 1: Study Schematic

Abbreviations: OLE = open-label extension.

All subjects will begin by receiving open-label SEP-363856 at the same dose they were taking upon completion of Study SEP361-308. Thereafter, the dose can be adjusted within the range of 50 to 100 mg/day, if deemed clinically necessary by the Investigator.

Dose adjustment criteria for SEP-363856 are described in Section 10.1.1.

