### 10.1.1. Dose Adjustment Criteria for SEP-363856

All subjects will begin by receiving open-label SEP-363856 at the same dose they were taking upon completion of Study SEP361-308. Thereafter, the dose can be adjusted within the range of 50 to 100 mg/day, if deemed clinically necessary by the Investigator.

Dose increases are to be made in increments of 25 mg (up to a maximum dose of 100 mg/day) no more frequently than weekly if the response to the previous dose level is not adequate and there are no significant tolerability problems, based on Investigator judgment. Increases in SEP-363856 dose will occur at regularly scheduled study visits, when possible. Dose increases between regularly scheduled visits may occur; however, the subject must return to the clinic for an unscheduled visit for drug dispensation (see Section 11.6.10).

The SEP-363856 dose can be decreased at any time in 25 mg increments as needed for safety or intolerability concerns as judged by the Investigator. If a dose decrease is needed between study visits, subjects will be asked to return to the clinic for an unscheduled visit for drug dispensation (see Section 11.6.10).

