## 10.2. Treatment Compliance

The Investigator will record the dose of the study drug and the date and time of the initial and final administration for each visit.

Compliance must be monitored closely and determined at each visit. Subjects will be instructed to bring all used blister cards and unused study drug with them to each visit. Compliance will be assessed by counting tablets and dividing the actual number of doses taken (per tablet count) by the number of doses the subject should have taken within a visit period and multiplying by 100. All subjects will be reminded of the importance of strict compliance with taking study drug. Subjects who take less than 75% of scheduled doses or take more than 125% of the scheduled doses during their entire participation in the study will be considered noncompliant. Evidence of noncompliance must be immediately reported to the Clinical Research Associate (CRA) and/or Medical Monitor.

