## 15.3.2. Study Drug Exposure and Compliance

Duration of exposure and compliance during the open-label extension treatment period will be summarized for the safety population.

Duration of exposure (in days) will be calculated as: last extension study dose date - first extension study dose date + 1. Duration of exposure will be summarized both as a continuous variable and categorically:

- Number and percentage of subjects with the open-label extension study drug exposure  $\geq 1, \geq 14, \geq 28, \geq 42, \geq 90, \geq 120, \geq 150$  days;
- Number and percentage of subjects with the open-label extension study drug exposure for 1 13, 14 27, 28 41, 42 89, 90 119, 120 149,  $\ge 150$  days

Percent compliance will be calculated overall for the open-label extension treatment period as: (number of tablets taken / number of tablets should have been taken)  $\times$  100%. Non-compliance is defined as less than 75% or more than 125% non-missing compliance for the open-label extension treatment period. Subjects with missing compliance will not be classified as non-compliant. Percent compliance will be summarized both as a continuous variable and

categorically (ie, number and percentage of subjects in each compliance category: < 75%, 75% - 125%, > 125%, and missing).

Mean daily dose will be calculated for the entire open-label extension treatment period as the cumulative dose (mg) of SEP-363856 divided by the duration of exposure (in days), where cumulative dose is the sum of all doses a subject received during the open-label extension treatment period. Modal daily dose will be determined as the daily dose that is taken for the most time (in terms of number of days) among all doses taken. Both mean daily dose and modal daily dose will be summarized.

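### The all-AE table by modal daily dose groups subjects by a dose that AEs themselves change, so it can flatten, hide or, if reductions are frequent, reverse a dose-AE relation

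*Protocol*

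**What the plan says.** Section 15.3.6.2 of the protocol states that "summaries of all AEs, SAEs, and AEs leading to discontinuation by modal daily dose will be provided". Section 15.3.2 supplies the grouping variable: "Modal daily dose will be determined as the daily dose that is taken for the most time (in terms of number of days) among all" of a subject's doses, counted over the extension treatment period.

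Three other places determine how that variable behaves:

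- Section 7.1, starting dose: "All subjects will begin by receiving open-label SEP-363856 at the same dose they were taking upon completion of Study SEP361-308".
- Section 10.1.1, downward: "The SEP-363856 dose can be decreased at any time in 25 mg increments as needed for safety or intolerability concerns".
- Section 10.1.1, upward: the dose may be raised "if the response to the previous dose level is not adequate and there are no significant tolerability problems".

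Section 12.3 includes a dose reduction among the actions that can be recorded for an AE, and section 7.4 lists tolerability reductions among the measures meant to keep subjects in the study. The protocol names no other AE summary by dose. The SAP is not available.

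**The concern.** Modal dose is known only once follow-up is over, and section 10.1.1 makes it respond to AEs in both directions. Events move subjects into lower-dose columns and keep others out of higher ones. The table therefore groups subjects by something that is partly a result of the outcome, and a larger sample would not cure that. It also takes no account of how long each subject spent on each dose.

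The question is a live one in this programme. Section 7.3.2 reports that 5 of 9 subjects at 100 mg/day in Study SEP361-106 had multiple moderate related AEs. Whether AEs become more frequent at 100 mg is what a reader of this extension will want to know, and the modal-dose table is the only by-dose AE display the protocol names. It could show little gradient where there is one, or fewer events at the higher dose where dose has no effect.

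The concern is with the all-AE table. An AE that ends treatment is followed by no further dosing, so the reduction mechanism hardly touches that table. No claim is made about SAEs.

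**Working it through.** **Planned size.** 120 × 0.75 × 0.75 = 67.5, which agrees with the stated figure of about 67. The protocol gives no AE rate by dose, no reduction rate and no split of starting doses, so everything below rests on assumed inputs. Triplets are in the order 50/75/100 mg.

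**By hand.** Assume 13/27/27 subjects start on each dose with AE risks 30/40/50%, giving 3.9/10.8/13.5 subjects with an AE. Let a share q of AEs at 75 and 100 mg lead to a 25 mg reduction, and let 70% of those reductions come early enough to change the modal dose. At q = 30% the share moved down is 0.30 × 0.70 = 0.21:

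- Leaving 100 mg: 0.21 × 13.5 = 2.835. Leaving 75 mg: 0.21 × 10.8 = 2.268.
- 100 mg: (13.5 − 2.835)/(27 − 2.835) = 44.1%
- 75 mg: (10.8 − 2.268 + 2.835)/(27 − 2.268 + 2.835) = 41.2%
- 50 mg: (3.9 + 2.268)/(13 + 2.268) = 40.4%

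A true 30/40/50% is displayed as 40/41/44%. At q = 50% the same sums give 46/42/39%, which is reversed.

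**Simulation A** (200,000 subjects, weekly steps, 24 weeks). Assumed: 4-week AE probability 8/12/24%; starting doses 20/50/30%; 15% of AEs stop treatment; a share q lead to a 25 mg reduction; 5% weekly increases, only before any AE; 1.2% weekly dropout for other reasons. The weekly AE probability is 1 − (1 − p)^(1/4), that is 2.1/3.1/6.6 per 100 patient-weeks, a 3.2-fold rise from 50 to 100 mg.

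| q | Any AE by modal dose, % |
|---|---|
| 10% | 46/55/69 |
| 30% | 55/58/65 |
| 40% | 58/58/62 |
| 50% | 62/59/60 |
| 60% | 64/59/57 |
| 80% | 69/60/52 |

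Of subjects whose first AE was on 100 mg, 18%, 33% and 51% are filed under a lower dose at q = 10%, 30% and 60%. AEs leading to discontinuation keep their order (6.2/10.8/17.2% at q = 60%). With no true dose effect (12% per 4 weeks at every dose), the all-AE table still shows 55/50/43% at q = 10% and 69/49/34% at q = 60%.

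**Sensitivity to the increase rule.** With no increases, q = 60% gives 56/47/62%. With 10% weekly increases it gives 71/69/56%. If an AE blocks increases for only 4 weeks, it gives about 61/59/61%.

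**Simulation B** (first AEs only, starting doses 20/40/40%, hazard ratio 1.25 per 25 mg, 50% risk at 100 mg). With no reductions the modal-dose table shows the true 36/43/50%. With AEs concentrated early:

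| q | Any AE by modal dose, % | Chance that 100 mg falls below 50 mg, 67 subjects |
|---|---|---|
| 0% | 36/43/50 | 20% |
| 10% | 41/43/47 | 33% |
| 30% | 48/44/41 | 66% |
| 50% | 54/45/34 | 91% |

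With onset spread evenly, q = 30% gives 44/43/45% and reversal comes at about q = 50% (48/44/41%). At hazard ratio 1.5 with even onset it comes only at q = 70% (43/41/37%).

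**Dose at onset.** In simulation B, first AEs per 100 subject-24-weeks by dose at onset stay at about 51/66/86 whatever q is. That run leaves out differences in susceptibility. Simulation A was therefore repeated with a gamma multiplier on the AE hazard (mean 1, variance 1) and 8 prior weeks under the same rules, keeping only those still on treatment:

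| True effect | q | Modal dose, % with any AE | Onset dose, AEs per 100 patient-weeks |
|---|---|---|---|
| Yes | 10% | 42/47/49 | 2.5/3.2/4.8 |
| Yes | 30% | 52/49/43 | 2.8/3.1/4.3 |
| Yes | 60% | 59/48/34 | 3.0/2.9/3.7 |
| None | 60% | 63/42/23 | 4.4/2.9/2.1 |

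**Precision.** With about 22 subjects per column (assumed equal split) and a 50% rate, the 95% half-width is 1.96 × √(0.5 × 0.5/22) = 0.21, or 21 points.

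**The case against.** The protocol sets no dose-response objective and plans no test. Analysis is for the overall group, the modal-dose table is a descriptive extra, and its definition is open. This stands and limits the importance of the point. It does not change what the table shows to anyone who reads across its columns.

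It can be said that a missing onset-dose summary is SAP content and so no defect of the protocol. The absence alone would not be a finding. But the protocol itself fixes the modal-dose grouping, and an added SAP table would not remove it.

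The strongest objection is that the reversal depends on assumptions. Simulation A lets any AE block increases permanently, whereas section 10.1.1 refers to significant tolerability problems judged by the investigator. Its 5% weekly increase also compounds to 1 − 0.95^24 = 71% over 24 weeks. With a 4-week block, or with no increases, 60% reductions do not put 100 mg lowest. This stands: no single threshold for reversal can be given. Attenuation, and the false inverse gradient where dose has no effect, do not need the permanent block. Simulation B has no increases at all and still reverses.

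Finally, rates by dose at onset are also confounded: they shrink a real effect and can show a false inverse one. This is true. In the true-effect runs they nevertheless kept 100 mg highest, and in the no-effect run they misled less than modal dose. The need for new tables is also weaker for SAEs and for AEs leading to discontinuation than for all AEs.

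**Conclusion.** The concern holds, as a low-priority point that is cheap to put right. The protocol groups AEs by a dose that AEs can lower or hold down, so its all-AE table by modal dose cannot be relied on to show a dose relation. The direction follows from sections 10.1.1, 15.3.2 and 15.3.6.2 alone. The size is unknown. Under the assumptions tried, the table is close to right when reductions are rare or late. Order is lost or reversed when somewhere between about 20% and 60% or more of AEs lead to a reduction, depending on when AEs start, how steep the true relation is, how freely doses rise and how much subjects differ in susceptibility. The primary endpoint, overall incidence in the safety population, is unaffected. With about 67 subjects, any by-dose figure will be imprecise.

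**What to change.** Add, preferably in the SAP, a summary of AEs by the dose being taken at onset, with patient-time on that dose as denominator (events per 100 patient-weeks). It is needed mainly for all AEs; SAEs and AEs leading to discontinuation can follow the same layout. Keep the modal-dose tables as a secondary display, with a note that they do not support comparison of AE frequency between doses. State that the onset-dose rates are also descriptive: doses are not randomised, and subjects on 100 mg are already selected for tolerating it.

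The data are already collected. Section 10.2 says "The Investigator will record the dose of the study drug and the date and time of the initial and final administration for each visit", and section 11.6.10 requires a clinic visit for any dose change between scheduled visits. In the SAP the cost is one table shell and its programming. Editing section 15.3.6.2 itself would be an amendment needing sponsor and IRB/IEC approval under section 17.5. Two drawbacks remain: late-onset events are credited to the current dose, and selection by tolerability can still understate a dose effect or suggest a false inverse one.
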